## 9.5.1.9.2 Barnes Akathisia Rating Scale

The BARS assessment consists of four items related to akathisia: objective observation of akathisia by the investigator, subjective feelings of restlessness by the subject, subject distress due to akathisia, and global evaluation of akathisia. The first three items were rated on a 4-point scale, with a score of zero representing absence of symptoms and a score of three representing a severe condition. The global clinical evaluation was made on a 6-point scale, with zero representing absence of symptoms and a score of five representing severe akathisia.

#### 9.5.1.9.3 Simpson Angus Scale

The SAS assessment consists of a list of 10 symptoms of parkinsonism (i.e., gait, arm dropping, shoulder shaking, elbow rigidity, wrist rigidity, head rotation, glabella tap, tremor, salivation, and akathisia). Each item was rated on a 5-point scale, with a score of one representing absence of symptoms, and a score of five representing a severe condition. The SAS Total Score was the sum of the scores for all 10 items.

## 9.5.1.10 Pharmacokinetic/Pharmacodynamic Assessments

Not applicable.

#### 9.5.2 Schedule of Assessments

The Schedule of Assessments for the study is provided in Table 3.

Final; 26 Feb 2018 Page 46 of 80

**Table 3:** Schedule of Assessments

Visit			1	2	3	4	5	6	7	8 q
Study Period	Screening/ Assessment	Phase A (Oral Tolerability Phase a )	Phase B (Treatment Phase)							
Day	Variable	-3 to -1	Baseline Day 1 b,g	15 g	30	60	90	120	150	180
Week				2 e	4	8	12	16	20	24
Procedure										
Informed consent	X									
Confirmation of diagnosis of schizophrenia (DSM-5)	X									
Review inclusion/and exclusion criteria	X									
Demographic information	X									
Complete medical history	X									
Complete psychiatric history c	X									
Antipsychotic therapy – current use and history d	X									
Electrocardiogram	X									
Urine pregnancy test e	X									X
Documentation of psychiatric and non-psychiatric hospitalizations and interventions f	X									
Contact from the CSW/SC via telephone or in-person g			Xg	Xg						
Clinical interview and mental status examination h					X	X	X	X	X	X
Vital signs i	X		X	X	X	X	X	X	X	X
Height, weight, BMI j	X		X	X	X	X	X	X	X	X
Screening or safety clinical laboratory testing as needed k,l,m	Xm		Xr	Xr	Xr	Xr	Xr	Xr	Xr	Xr
Fasting lipid profile n	X		X		X		X			X
HbA1c 	X		X		X		X			X
Prolactin k			X		X					X
CGI-I			X	X	X	X	X	X	X	X

Final; 26 Feb 2018 Page 47 of 80

**Table 3:** Schedule of Assessments

Visit			1	2	3	4	5	6	7	8 q
Study Period	Screening/ Assessment	Phase A (Oral Tolerability Phase a )	Phase B (Treatment Phase)							
Day	Variable	-3 to -1	Baseline Day 1 b,g	15 g	30	60	90	120	150	180
Week				2 e	4	8	12	16	20	24
Procedure										
CGI-S	X									
AIMS, BARS, SAS	X		X	X	X	X	X	X	X	X
PSP			X							X
C-SSRS o	X		X	X	X	X	X	X	X	X
Oral aripiprazole treatment a,p		X	X							
Administer aripiprazole once monthly			X		X	X	X	X	X	X
Injection site assessment			X		X	X	X	X	X	X
Reporting of AEs	X	X	X	X	X	X	X	X	X	X
Concomitant medications	X	X	X	X	X	X	X	X	X	X

AE = adverse events, AIMS = Abnormal Involuntary Movement Scale, ALP = alkaline phosphatase, ALT = alanine transaminase, AST = aspartate transaminase, BARS = Barnes Akathisia Rating Scale, BMI = body mass index, BUN = blood urea nitrogen, CBC = complete blood count, CGI-I = Clinical Global Impression—Improvement, CGI-S = Clinical Global Impression—Severity, C-SSRS = Columbia Suicide Severity Rating Scale, CSW = community support worker, DSM-5 = Diagnostic and Statistical Manual, Fifth Edition, ECG = electrocardiogram, ED = emergency department, HbA1c = glycosylated hemoglobin, HDL = high-density lipoprotein, Hgb = hemoglobin, ICF = Informed Consent Form, LDL = low-density lipoprotein, MO = Missouri, PSP = Personal and Social Performance Scale, SAS = Simpson Angus Scale, SC = Study Coordinator, ULN = upper limit of normal

Note: Baseline was considered Day 1, or first day of long-acting injectable treatment in the hospital, of Phase B. However, some subjects may have had their baseline assessments (including clinical laboratory tests) performed any time during or immediately after treatment with oral antipsychotic aripiprazole (unless eligible to skip Phase A in which it was any oral antipsychotic), ideally prior to starting long-acting injectable aripiprazole. Participants were allowed, with Principal Investigator approval, to enter the study after starting treatment with long-acting injectable aripiprazole in the hospital and baseline assessments were performed as soon as feasible within 48 hours of hospital discharge.

Final: 26 Feb 2018

<sup>a The Oral Tolerability Phase lasted for a minimum of 3 days. Subjects who had history of tolerability (e.g., taking at least 3 consecutive doses) with oral aripiprazole and no history of intolerance could receive their aripiprazole once monthly injection immediately upon completion of the screening procedures. All subjects received the first injection of aripiprazole once monthly at Baseline, Day 1.

b: Discharge could occur at any time after the first injection of aripiprazole once monthly.

<sup>ct The complete psychiatric history included a diagnosis reconciliation form on which information from medical records and a clinical interview by a study clinician were recorded.

d: Previous medications taken within 7 days prior to starting study drug and all central nervous system-active compounds taken within 30 days preceding the first dose of study drug were recorded. All antipsychotic medications used within 6 months of screening were recorded.

e: A urine pregnancy test was performed for women of childbearing potential only at screening, Visit 10, and at the Follow-up visit; subsequent testing was done as is clinically indicated. If a subject or investigator suspected that the subject may be pregnant, a serum pregnancy test would then be performed.

**Table 3:** Schedule of Assessments

Visit				2	3	4	5	6	7	8 q
Study Period	Screening/ Assessment	Phase A (Oral Tolerability Phase a )			Pha	nse B (Trea	tment Ph	ase)		
Day	Variable	-3 to -1	Baseline Day 1 b,g	15 g	30	60	90	120	150	180
Week				2 e	4	8	12	16	20	24
Procedure										

- f: Data regarding psychiatric and non-psychiatric hospitalizations and medical interventions occurring within the 6 months prior to the date of the signing the ICF were obtained by searching MO HealthNet (Medicaid) and MO Department of Mental Health (DMH) data via collaboration with the Missouri Institute of Mental Health (MIMH); availability of Medicaid data and documentation of at least one inpatient hospitalization or ED visit within the previous 6 months was required for eligibility.
- g: For subjects who were psychiatrically stabilized and discharged prior to the completion of the required 14-day course of oral aripiprazole, a pre-discharge assignment was given to a CSW or SC. The CSW/SC maintained regular contact with the subject until the Week 2 visit. Following the Week 2 visit, subjects had contact with their assigned CSW/SC based on routine clinical care.
- h: At all outpatient visits, scheduled or unscheduled.
- i: Vital signs were recorded daily while hospitalized.
- j: BMI was calculated as: mass (kg)/height (m2).
- k: Subjects should have been fasting for a minimum of 10 hours prior to blood draws for all laboratory assessments. Every effort was made to obtain the clinical laboratory samples at the same time of day at each visit. All laboratory testing was performed at local laboratories at the clinical sites.
-  Safety clinical laboratory testing was conducted at screening, and as deemed clinically necessary thereafter. Standard clinical safety laboratory testing included: hematology (CBC with differential, and platelet count), chemistry (ALT, albumin, ALP, AST, total bilirubin, BUN, calcium, chloride, creatinine, glucose, potassium, serum prolactin, total protein, and sodium). Urinalysis was a dipstick with microscopic as clinically indicated.
- m: Exclusionary tests at screening were: platelets  $\leq 75,000 \text{ mm3}$ , Hgb  $\leq 9 \text{ g/dL}$ , fasting glucose > 126 mg/dL, HbA1c > 7.0%, absolute neutrophils  $\leq 1,000/\text{mm3}$ , ALT > 3x ULN, AST > 3x ULN, creatinine  $\geq 2 \text{ mg/dL}$ , diastolic blood pressure > 105 mm Hg, QTc > 475 msec on either the Bazett or Fridericia corrections on ECG, any other abnormal findings that would affect the safety of the subject or interpretation of the study results (Section 9.3.2).
- n: Lipid profile included: total cholesterol, HDL cholesterol, LDL cholesterol, and triglycerides.
- o: At screening the baseline C-SSRS was completed, at subsequent visits, the "since last visit" version was completed.
- P: All subjects received 14 days of oral aripiprazole beginning with the first dose of aripiprazole once monthly.
- q: All subjects who completed or withdrew from the study received a telephone call for safety follow-up at 30 (± 5) days after the last study visit unless they withdrew their consent for participation in the study to assess for any AEs experienced since the last visit (Section 9.1.4.3).
- r: Clinical laboratory testing only as needed for safety purposes, as determined by the Principal Investigator.

Final: 26 Feb 2018

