#### 9.1.4.2 Treatment Phase

Eligible subjects who had a history of tolerating oral aripiprazole or were currently taking oral aripiprazole entered Phase B directly from the Screening Period. All other subjects entered Phase B following successful completion of Phase A. After the baseline assessments were completed, the subject received the first aripiprazole once monthly IM injection, in conjunction with the first of 14 doses of concomitant oral antipsychotic medication (see Figure 1). Use of concomitant oral aripiprazole during this lead-in was per the investigator's judgment based on the prescribing instructions.

All subjects must have attended scheduled visits at the Baseline Visit and Weeks 2, 4, 8, 12, 16, 20, and 24, totaling 180 days. Aripiprazole once monthly injections occurred at the Baseline Visit and every 28 (-2, +5) days at Weeks 4, 8, 12, 16, 20, and 24, totaling seven injections. After the

Final; 26 Feb 2018 Page 28 of 80

initial injection of 400 mg, the monthly dosage could be decreased to 300 mg, based on the clinical judgment of the investigator. All aripiprazole once monthly injections were administered based on the investigator's judgment and the prescribing information. For subjects who entered the studies after starting the first dose of long-acting injectable aripiprazole in the hospital, if the initial injection was not 400 mg, the second injection should have been 400 mg, and thereafter, the monthly dose could be decreased to 300 mg, based on clinical judgment of the investigator.

For subjects who were psychiatrically stabilized and discharged prior to the completion of the required 14-day course of oral antipsychotic medication, a pre-discharge assignment was given to a CSW/SC. The CSW/SC maintained regular contact with the subject until the first outpatient visit in Phase B (Week 2), when oral aripiprazole was discontinued. Regular contact was defined as no less than weekly, but could have been more frequent depending on the clinical judgment of the CSW/SC and outpatient treatment team. Following the Week 2 Visit, subjects were to have contact with their assigned CSW/SC based on routine clinical care. Contact with the CSW/SC could be in person or by telephone, as clinically appropriate.

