## 9.1.4.3 Early Termination

All subjects who completed or withdrew from the study received a telephone call for safety follow-up at 30 ( $\pm$  5) days after the last study visit unless they withdrew their consent for participation in the study. This telephone contact was made to assess if there were any AEs experienced since the last visit. In addition, the subject was asked about any new medications or changes in existing medications and the information was documented in the source documentation. The study site registered the contact in the interactive voice response system or interactive web response system.

The end of the study was the date of the last study visit for the last subject.

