#### 9.5.1.5 Adverse Events and Other Events of Interest

An AE is any untoward medical occurrence in a subject or clinical investigation subject administered a drug under study. An AE does not necessarily have a causal relationship with the study drug. For this study, the study drug was aripiprazole once monthly and oral aripiprazole.

The criteria for identifying AEs were:

- Any unfavorable and unintended sign (including an abnormal laboratory finding), symptom, or disease temporally associated with the use of a drug under study, whether or not considered related to the drug under study
- Any new disease or exacerbation of an existing disease

Final; 26 Feb 2018 Page 40 of 80

LDL = low-density lipoprotein

a: Triglycerides were measured at screening only, to rule out exclusionary values

b: Serum β-hCG was performed if the subject or investigator suspected that the subject may be pregnant

- Any deterioration in nonprotocol-required measurements of a laboratory value or other clinical test (e.g., ECG or x-ray) that results in symptoms, a change in treatment, or discontinuation of study drug
- Recurrence of an intermittent medical condition (e.g., headache) not present pretreatment (i.e., baseline)
- An abnormal laboratory test result was considered an AE if the identified laboratory abnormality led to any type of intervention, whether prescribed in the protocol or not.

A laboratory result was to be considered by the investigator to be an AE if it:

- Resulted in the withdrawal of study drug
- Resulted in withholding of study drug pending some investigational outcome
- Resulted in an intervention, based on medical evaluation (e.g., potassium supplement for hypokalemia)
- Resulted in any out of range laboratory value that in the investigator's judgment fulfills the definitions of an AE with regard to the subject's medical profile

All AEs observed during the study were reported on the CRF. All AEs, regardless of relationship to study drug or procedure, were collected beginning from the time the subject signed the study ICF through the last visit. Serious AEs were collected for 30 days after the last dose or at the Follow-up Visit, whichever came later.

Abnormal laboratory values were not listed as separate AEs if they were considered to be part of the clinical syndrome that is being reported as an AE. Any laboratory abnormality considered to constitute an AE was reported as an AE on the CRF.

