## 9.5.4 Reporting of Serious Adverse Events, Pregnancy, and Other Events of Interest

Collection of safety information was completed from the first administration of the study drug until 28 days after discontinuation, unless otherwise specified in the protocol. The longer of the two timeframes was employed if there was a conflict.

Safety information was defined as any information from any source containing information such as:

- AE or suspicion thereof
- Lack of efficacy
- Overdose/incorrect dosage (i.e., accidental or intentional)
- Abuse/misuse (e.g., patients sharing medication); even without resulting adverse reaction
- Accidental exposure (e.g., child takes parent's medication)
- Medication error
- Withdrawal reactions
- Disease progression/exacerbation of existing disease
- Drug-drug/drug-food interactions
- Exposure to drug during pregnancy, where the embryo or fetus may have been exposed to medicinal products either through maternal exposure or transmission of a medicinal product via semen following paternal exposure
- Exposure to drug during lactation, including uneventful
- Suspected counterfeit product
- Suspected transfer of infectious disease/agent by the medicinal product concerned
- Product Quality Complaint (PQC) with safety related/medically important information
- Pediatric use, if not an approved use

Final; 26 Feb 2018 Page 50 of 80

- Occupational exposure
- Off-label use

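### The permitted window for the closing safety call does not guarantee active questioning through the 30-day SAE collection period

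*Combined protocol and SAP*

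**What the plan says.** Section 9.1.4.3 and Table 3 footnote q provide one contact after the final visit: subjects who completed or withdrew "received a telephone call for safety follow-up at 30 (± 5) days after the last study visit", unless they had withdrawn consent. Section 9.1.4.3 gives its purpose: "This telephone contact was made to assess if there were any AEs experienced since the last visit". It also defines study end: "The end of the study was the date of the last study visit for the last subject". The call therefore comes after the last scheduled visit, and Table 3 lists nothing beyond it.

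The collection periods are set elsewhere. Section 9.5.1.5 states: "Serious AEs were collected for 30 days after the last dose or at the Follow-up Visit, whichever came later". Section 9.5.4 collects safety information "until 28 days after discontinuation, unless otherwise specified in the protocol", and adds: "The longer of the two timeframes was employed if there was a conflict".

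Section 9.1.4.2 places the injections at baseline and then "every 28 (-2, +5) days at Weeks 4, 8, 12, 16, 20, and 24, totaling seven injections". Week 24 is Visit 8, the final column of Table 3. Section 9.5.1.5 also fixes what counts as a dose: "For this study, the study drug was aripiprazole once monthly and oral aripiprazole".

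A Follow-up Visit is named in Section 9.5.1.5 and in Table 3 footnote e (pregnancy test), but Table 3 has no such column. Amendment 1.0 records that the follow-up period was removed.

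**The concern.** The call is the only planned occasion on which a subject is asked about events after the last visit. Its window is centred on Day 30 and so opens before the SAE period closes. A site can call early, stay within the window, and never ask about the end of the period.

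What is at stake is completeness of SAE ascertainment after the last depot injection. Inpatient hospitalization is an SAE criterion in Section 9.5.1.6, and psychiatric admission is not among the listed exceptions. An admission shortly after an early call would be captured only if someone volunteered it.

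**Working it through.** The plan gives no figure to reproduce. The check is day arithmetic.

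**Inputs**
- Call window (9.1.4.3; Table 3 footnote q): 30 − 5 = Day 25 to 30 + 5 = Day 35 after the last visit, so 35 − 25 + 1 = 11 permitted days.
- SAE period (9.5.1.5): at least 30 days after the last dose. Because the later of the two limits applies, an earlier contact cannot shorten it.
- L = days from last dose to last visit. For a completer L = 0, since the seventh injection is given at Visit 8 (9.1.4.2; Table 3).

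**Formula.** A call c days after the last visit falls L + c days after the last dose. Days not covered by questioning = max(0, 30 − (L + c)).

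**Completer (L = 0)**

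| Call day c | 25 | 26 | 27 | 28 | 29 | 30 to 35 |
|---|---|---|---|---|---|---|
| Days not asked about | 5 | 4 | 3 | 2 | 1 | 0 |

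Five of the 11 permitted days (5/11 = 45%) leave a gap, and six leave none.

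**Last visit after the last dose (L > 0).** With the earliest call, c = 25, the gap is max(0, 5 − L): 4, 3, 2, 1 and 0 days for L = 1, 2, 3, 4 and 5. From L = 5 on, every permitted call covers the 30 days. A withdrawing subject whose last visit was a dosing visit has L = 0 and is in the same position as a completer.

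**Last dose after the last visit (L < 0).** Oral aripiprazole counts as study drug, and footnote p gives 14 days of it from the first injection. Suppose a subject's last visit was Day 1 and the oral course was then finished on Day 14. The last dose is 14 − 1 = 13 days after the last visit, so L = −13 and the gap is 30 − (c − 13) = 43 − c. That is 18 days for a call on Day 25 and 8 days for a call on Day 35. The case is hypothetical but the text permits it, and it shows that the starting point of the clock matters as well as the width of the window.

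**Other scheduled contacts.** The Synopsis still mentions a 30-day follow-up period, but as a duration without a visit. Contact with the community support worker or study coordinator continues after Week 2 according to routine care; the documents do not say whether it extends beyond the last visit.

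**The case against.** The strongest reply is that the rules do not contradict each other. A call on Days 30 to 35 satisfies Sections 9.1.4.3, 9.5.1.5 and 9.5.4 together for a completer. That stands. A reader might infer that a site can obey one rule only by breaking the other, or that the SAE period cannot be met; the documents support neither.

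A reader might also infer that an early call ends observation. It does not. Nothing says the call closes collection, and under Section 9.5.1.5 collection stays formally open to Day 30. Section 9.5.4 accepts information from any source. What is missing after an early call is scheduled questioning.

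Three ways of enlarging the point also fail.
- The 28-day period adds nothing for SAEs. It covers safety information generally and yields to the longer period. Calls on Days 25 to 27 precede Day 28, but those days are already among the five counted.
- The 45% is a share of calendar days in the window. It is not a share of subjects or of missed events. An average loss of (5 + 4 + 3 + 2 + 1)/11 = 1.4 days per completer would require calls spread evenly over the window, which the documents do not suggest, since the target is Day 30.
- Psychiatric hospitalization is both the primary event and an SAE, so a reader might fear for the primary endpoint. The call is not named as a source of endpoint data, and no effect on that endpoint follows.

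Some text under Section 9.5.4.1 was not available to this review, so a further reporting instruction there cannot be excluded.

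**Conclusion.** The point holds in limited form: the permitted call window does not guarantee active questioning through the SAE collection period. For a completer the shortfall is 1 to 5 of 30 days when the call is made on Days 25 to 29, and nothing otherwise. This rests on three readings: last dose and last visit coincide at Week 24; the 30 days are a minimum; and the call is the only scheduled contact after the last visit, with the unscheduled Follow-up Visit being either this call or a remnant of the removed period.

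Severity is minor. In this trial the practical effect is smaller still: it was terminated for slow enrollment, and Tables 7 and 8 show data from one subject at Day 180. Withdrawn subjects whose last visit included an injection are exposed to the same gap.

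**What to change.** In Section 9.1.4.3 and Table 3 footnote q, set the call at 30 (+5) days after the later of the last visit and the last dose. The call then falls at least 30 days after the last dose in every case: L + 30 or more days when L is zero or positive, and 30 to 35 days when the last dose is the later date. Narrowing the window without changing its starting point would leave the L < 0 case open.

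In Section 9.5.1.5 and Table 3 footnote e, either identify the Follow-up Visit with this call or delete the term. Footnote e attaches a urine test to that visit, which a telephone call cannot deliver, so the two must be reconciled. In the same edit, reconcile the statement in Section 9.5.1.5 that all AEs are collected through the last visit with the call's purpose of asking about AEs since then.

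The cost is a change of window and starting point in two places, plus the tidying of one term. Sites lose Days 25 to 29 for scheduling. As the study has ended, the text change serves any reuse of the protocol; for this report, the sponsor could state each call date relative to the last dose and identify any subject not questioned through Day 30.

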# Safety:

- To evaluate changes from baseline to 180 days in:
  - o AEs
  - Clinical laboratory tests (i.e., hematology, fasting clinical chemistry, prolactin, and urinalysis)

Final; 26 Feb 2018 Page 21 of 80

Clinical Study Report: Collaborative Protocol [contact] ClinicalTrials.gov Identifier: NCT02717130

- o Vital signs
- o PSP
- o Injection site reactions (i.e., localized pain, redness, swelling, and induration)
- o EPS:
  - Abnormal Involuntary Movement Scale (AIMS)
  - Simpson-Angus Scale (SAS)
  - Barnes Akathisia Rating Scale (BARS)
- o Columbia Suicide Severity Rating Scale (C-SSRS) for suicidality

Final; 26 Feb 2018 Page 22 of 80

ClinicalTrials.gov Identifier: NCT02717130

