## 9.5.1.4 Safety Assessments

Safety was assessed by AE reporting, clinical laboratory tests (i.e., hematology, fasting clinical chemistry, and lipid profile), urinalysis, urine pregnancy testing and vital signs measurements. In addition, body weight, BMI, and serum prolactin concentrations were monitored.

The following scales were used to assess for EPS:

- AIMS
- SAS
- BARS

For subjects receiving an injection, the investigator, or qualified designee, assessed the injection site for localized pain, redness, swelling, and induration.

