## 9.7.1.8 Safety Analyses

All safety analyses were to be performed on the Safety Analysis Sets. Safety data were summarized on an "as treated" basis using descriptive statistics (e.g., n, mean, standard deviation, median, minimum, maximum for continuous variables; and n [%] for categorical variables). Safety variables included TEAEs, clinical laboratory parameters, vital signs, and 12-lead ECG results. Study Day 1 for all safety analyses was defined as the date of the first dose of study drug.

In general, baseline measurements of safety variables were defined as the last measurements prior to the first dosing of study drug for each phase of the study. Safety analyses were conducted based on the safety populations (Section 9.7.1.4).

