## 9.7.1.8.2 Laboratory Values

Laboratory results were to be summarized using Système International units, as appropriate. For all quantitative parameters listed in Section 9.5.1.4 Safety Assessments, the actual value and the change from baseline to each post-baseline visit and to the end of treatment (i.e., defined as the last on-treatment value) was summarized using descriptive statistics. Qualitative parameters listed

Final; 26 Feb 2018 Page 55 of 80

in Section 9.5.1.4 were summarized using frequencies (i.e., number and percentage of subjects), and changes from baseline to each post-baseline visit and to end of treatment were reported. Percentages were based on the number of subjects with both nonmissing baseline and relevant post-baseline results.

Laboratory test results were assigned a low/normal/high (LNH) classification according to whether the value was below (L), within (N), or above (H) the laboratory parameter's reference range.

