**Blood Chemistry Safety Laboratory Results Table 7:** 

		Timepoints							
			_	Phase B					
		Screening	Day 30	Day 120	Day 180				
Blood		(n=8)	(n=2)	(n = 3)	(n=1)				
Chemistry	Unit		Mean	(SDa)					
Albumin	g/dL	4.19 (0.43)	4.30 (0.42)	4.70 (0.26)	4.50				
Calcium	mg/dL	9.01 (0.71)	9.25 (0.64)	9.70 (0.20)	9.50				
BUN	mg/dL	10.88 (3.04)	12.50 (0.71)	12.33 (1.15)	13.00				
Total bilirubin	mg/dL	0.44 (0.16)	0.50 (0.42)	0.43 (0.21)	0.60				
ALP	U/L	68.88 (17.40)	68.00 (1.41)	80.33 (18.34)	68.00				
AST	U/L	17.50 (5.24)	16.50 (2.12)	16.33 (0.58)	22.00				
ALT	U/L	16.25 (4.17)	15.50 (0.71)	18.33 (5.86)	23.00				
Creatinine	mg/dL	0.76 (0.25)	0.87 (0.07)	0.99 (0.08)	0.86				
Sodium	mmol/L	139.88 (3.52)	140.50 (2.12)	141.00 (1.73)	141.00				
Potassium	mmol/L	4.08 (0.29)	4.05 (0.35)	4.27 (0.06)	4.00				
Chloride	mmol/L	102.25 (3.81)	104.00 (1.41)	103.00 (1.73)	104.00				
Carbon dioxide	mmol/L	25.38 (3.62)	25.00 (4.24)	23.67 (2.52)	26.00				
Fasting glucose	mg/dL	88.63 (10.36)	90.00 (9.90)	86.00 (16.46)	ND				
Total protein	g/dL	7.04 (0.82)	7.30 (0.71)	7.53 (0.50)	7.10				

ALP = alkaline phosphatase, ALT = alanine transaminase, AST = aspartate transaminase, BUN = blood urea nitrogen, ND = not done, SD = standard deviation

a: Standard deviations were not calculated for Day 180, these data were for an n of 1

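### By-visit change from baseline is planned for haematology, chemistry and urinalysis, and fasting glucose is modelled at Days 30, 90 and 180, but none of these has a scheduled on-treatment sample

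*Combined protocol and SAP*

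**What the plan says.** **Objective.** Section 8.3 sets out to evaluate change from baseline to 180 days in "Clinical laboratory tests (i.e., hematology, fasting clinical chemistry, prolactin, and urinalysis").

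**Analysis.** For the quantitative parameters of Section 9.5.1.4, Section 9.7.1.8.2 summarises "the actual value and the change from baseline to each post-baseline visit and to the end of treatment". For the qualitative ones it adds that "changes from baseline to each post-baseline visit and to end of treatment were reported". The parameters in Section 9.5.1.4 include "clinical laboratory tests (i.e., hematology, fasting clinical chemistry, and lipid profile), urinalysis, urine pregnancy testing and vital signs measurements".

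**Schedule.** Table 3 marks the safety laboratory row at Day 1 and at every Phase B visit, each mark carrying footnote r: "Clinical laboratory testing only as needed for safety purposes, as determined by the Principal Investigator". Footnote l says the same for haematology, chemistry and urinalysis, and the Treatment Phase text in Section 9.1.4.2 agrees.

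**Fasting glucose.** It is a secondary endpoint (Section 9.7.1.2), to be analysed by a repeated-measures mixed model at baseline, 30, 90 and 180 days (Section 9.7.1.9). It has no row in Table 3. Section 9.1.2 places a fasting glucose at the Baseline Visit, and footnote l puts glucose in the as-needed chemistry panel.

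**ECG.** Section 9.7.1.8 states: "Safety variables included TEAEs, clinical laboratory parameters, vital signs, and 12-lead ECG results". Table 3 has one ECG, at Screening.

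**The concern.** The analysis asks for values that the schedule does not secure. When sampling is left to judgement, the subjects with a value at a visit are not a defined sample of those on treatment at that visit. A mean change computed from them cannot answer whether laboratory values moved on aripiprazole once monthly, in either direction.

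Section 9.7.1.8.2 bases its percentages on subjects with non-missing baseline and post-baseline results, so untested subjects leave the denominator. The plan does not ask for the number attending or the reason for the test.

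Glucose matters more than the rest. It is a modelled secondary endpoint for cardiometabolic risk, and a mixed model cannot recover time points at which few or no samples were taken.

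**Working it through.** No power, alpha or sample-size figure bears on this point. The check sets the analysis text against the schedule, then looks at what was collected.

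**Step 1. Plan against schedule.**

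| Test | Analysis planned | Fixed sampling after screening |
|---|---|---|
| Haematology, chemistry, urinalysis | Change at each post-baseline visit, at end of treatment and to 180 days | None (Table 3, footnotes l and r) |
| Fasting glucose | Mixed model at baseline, 30, 90 and 180 days | Baseline Visit only (Section 9.1.2) |
| Lipids, HbA1c | Change from baseline | Days 1, 30, 90 and 180 |
| Prolactin | Change to 180 days | Days 1, 30 and 180 |
| ECG | Named for descriptive summary; no change by visit | None (Screening only) |

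The first two rows do not match. The lipid, HbA1c and prolactin rows do have scheduled samples. ECG is a smaller mismatch of a different kind.

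**Step 2. How many subjects were seen.** Table 8 gives means and SDs without n, except that its note states n = 1 at Days 150 and 180. With whole-number scores, mean = Σx/n and SD = √[Σ(x − mean)²/(n − 1)] restrict n:

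- Day 30 AIMS 0.20 (0.45): one of five subjects scoring 1 gives mean 1/5 = 0.20 and SD = √[(0.64 + 4 × 0.04)/4] = √0.20 = 0.45.
- Day 90 AIMS 0.25 (0.50): one of four scoring 1 gives mean 0.25 and SD = √[(0.5625 + 3 × 0.0625)/3] = √0.25 = 0.50.

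Enumerating all sets of whole-number scores for n = 2 to 8, AIMS and CGI-I each fit only n = 5 at Days 15, 30 and 60, and only n = 4 at Days 90 and 120.

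**Step 3. Chemistry reported (Table 7) over subjects rated.**

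- Day 30: 2/5 = 40%.
- Day 90: no column in Table 7, so none reported out of 4.
- Day 120: 3/4 = 75%.
- Day 180: 1/1. Table 7 notes: "Standard deviations were not calculated for Day 180, these data were for an n of 1".

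Of the three post-baseline glucose time points in the model, Table 7 has values only at Day 30 (column n = 2). Day 90 has no column and Day 180 glucose is marked not done.

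**Step 4. Comparison with a scheduled test.** I applied the same method to the Table 8 lipids, assuming whole mg/dL values and n from 2 to 5. At Day 30 the four lipids together fit only n = 4. For example, a triglyceride mean of 68.50 needs an even n. With n = 2 the values sum to 137, so their difference is odd; 33 or 35 gives SD 23.33 or 24.75, not the reported 24.09. At Day 90 each of the four lipids fits only n = 4. Scheduled lipids therefore reached 4 of 5 and 4 of 4 subjects, where as-needed chemistry reached 2 of 5 and none reported. Missed attendance does not explain the difference.

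**The case against.** **As-needed testing is defensible here.** This is a hospitalisation study of a marketed product used according to its labelling, and the laboratory tests are exploratory and descriptive. Section 9.7.1.8 already requires n with each summary, and no formal or safety analysis was run. All of this limits the consequence for the laboratory panel. It does not make a by-visit mean change interpretable, and it does not cover glucose, which is a modelled secondary endpoint.

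**Section 9.5.1.4.1 can be read as visit-based sampling with discretionary extras.** It says samples were taken at the visits designated in Table 3. But it defers to Table 3, and Table 3 makes the marks conditional.

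Four stronger readings are tempting, and the documents do not support them:

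- *Subjects were tested because something looked wrong.* No available text gives the reason for any draw. Every on-treatment mean in Table 7 lies within the LabCorp and Washington University ranges of Appendix 1. At Day 120 lipids and HbA1c were also reported, although Table 3 schedules neither there, which suits bundled draws at least as well. Discretionary sampling is established; selection by suspicion is only a possibility.
- *All on-treatment laboratory tests are as-needed.* Lipids, HbA1c and prolactin are not. Footnote l also lists prolactin in the as-needed panel, but prolactin has its own Table 3 row with fixed visits.
- *A by-visit ECG change is planned and cannot be delivered.* Section 9.5.1.4 does not list ECG, and no section plans an ECG change from baseline or an on-treatment QTc statement. Unscheduled ECGs could also occur.
- *Almost nobody was tested.* That holds only if Day 120 (3 of 4) and Day 180 (1 of 1) are left out.

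**Conclusion.** The point holds for haematology, chemistry, urinalysis and fasting glucose. The plan commits to change from baseline by visit, or to a model at fixed days, for tests with no guaranteed on-treatment sample. The resulting summaries would describe a discretionary subset whose representativeness cannot be judged.

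This conclusion rests on the text and Table 3 alone. The counts in the working are illustration: they are very small, attendance is inferred from rounded means and SDs, and the Day 90 figure rests on the absence of a column in Table 7.

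The mismatch is worth correcting, chiefly for glucose. Since the study stopped early without formal analysis, the practical effect now is on how Table 7 is read: it should not be taken as evidence that chemistry did or did not change on treatment. The ECG mismatch is a minor matter of wording.

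**What to change.** **Preferred.** Give fasting glucose its own row in Table 3 at Baseline and Days 30, 90 and 180. Run the Table 2 haematology and chemistry panel on the blood already drawn for lipids and HbA1c at Days 30, 90 and 180, with urinalysis at Day 180. Limit Section 9.7.1.8.2 to those visits for these tests, and amend footnotes l and r to match. No further Baseline panel is needed, because Section 9.7.1.8 takes the last pre-dose value as baseline and the Screening result can serve. The cost is modest: laboratory charges for three panels and one urinalysis per subject, plus glucose, with no extra blood-draw visits.

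**If the panel cost is not accepted.** Still schedule fasting glucose at the four modelled time points. For the other tests, replace the by-visit mean change with a listing of as-needed results showing number tested over number attending and the reason for each test. Reword the Section 8.3 objective accordingly. Apart from glucose, this is a wording change plus one recorded field for the reason.

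**ECG.** Report it as a screening or baseline characteristic rather than among the safety variables of Section 9.7.1.8. This costs nothing.
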